9.4.4 Handling of missing values/censoring/discontinuations

Patients who drop out prematurely and/or do not have a valid PASI assessment at Week 52 will be counted as non-responders. Patients with major protocol violations, but with a valid PASI assessment will be included in the ITT-analysis with their observed response.

The same algorithm will be used for the key secondary endpoint, the PASI 90 response in the FAS-P75P set. Missing values for other endpoints will not be replaced.

9.4.5 Supportive analyses

The primary analysis will be repeated for the Per-Protocol Set (PP-P90R). The impact of missing values will be explored using multiple imputation as a sensitivity analysis. The raw (unadjusted) response rates and their difference will be computed with the corresponding CI (option RISKDIFF in SAS PROC FREQ).

9.5 Analysis of secondary variables

9.5.1 Efficacy variables

The key secondary variable is the PASI 90 response rate at Week 52 in the FAS-P75P, ie, the proportion of patients with a PASI 75 response but also less than a PASI 90 response at Week 24 who achieve a PASI 90 response at Week 52. The key secondary analysis of this study will be to demonstrate superiority of the shortened 2-weekly dosing group compared to the 4-weekly dosing group in the FAS-P75P.

The statistical null-hypothesis to be rejected are that the odds ratio of gaining a PASI 90 response for patients on 2-weekly dosing versus patients on 4-weekly dosing = 1

Let π_i denote the probability of a PASI 90 response at Week 52 for treatment group j, j = 0, 1where

- 0 corresponds to 2-weekly dosing
- 1 corresponds to 4-weekly dosing

The following hypothesis will be tested

$$H_{0.2}$$
: $(\pi_0 / [1 - \pi_0]) / (\pi_1 / [1 - \pi_1]) = 1$ versus H_{A2} : $(\pi_0 / [1 - \pi_0]) / (\pi_1 / [1 - \pi_1]) \neq 1$

This analysis will be performed comparing dosing groups (Group 3 vs Group 4) with respect to the key secondary variable in a logistic regression model with the factors treatment, country and PASI response (75% to 82% or 83% to 89%) at Week 24. The odds ratio with its corresponding 95% CI and p-value will be presented.

The key secondary analysis will be included in a confirmatory testing strategy. The key secondary hypothesis will be a priori ordered below the primary hypothesis. This means that no multiplicity adjustment of the significance level is required; however, confirmatory evidence will be claimed only if non-inferiority with regard to the primary endpoint has been successfully demonstrated before. Otherwise, the result for the secondary endpoint will be interpreted as being purely explorative, independent of the nominal p-value.

The time course of PASI response (absolute points and percentage change from Baseline) will be graphically displayed for treatment Group 1 to 4 as well as for the total Treatment Period 1 set. All other secondary variables (IGA mod 2011, QoL) will be analyzed descriptively using means and SDs for continuous and absolute and relative frequencies for categorical variables.

Appropriate statistical tests for group comparisons of these variables will be defined in the SAP.

9.5.2 Safety variables

For safety-evaluations, the patient groups of PASI 90 responders and those who achieve PASI 75 but not PASI 90 will be pooled for Group 1 and Group 3; therefore, only 3 dosing groups will be compared:

- secukinumab 300 mg s.c. every 2 weeks (patients from Group 4).
- secukinumab 300 mg s.c. every 4 weeks (patients from Group 1 pooled with Group 3).

• secukinumab 300 mg s.c. every 6 weeks (patients from Group 2).

Patients will be analyzed according to the treatment they received.

Treatment emergent AEs (events started after the first dose of study drug or events present prior to the first dose of study drug but increased in severity based on preferred term) will be summarized. Only primary paths within MedDRA will be considered for AE reporting.

AEs will be summarized by presenting, for each treatment group, the number and percentage of patients

- having any AE,
- having an AE in each primary SOC and
- having each individual AE (preferred term).

Summaries will also be presented for AEs by severity and for study drug related AEs. If a patient reported more than one AE with the same preferred term, the AE with the greatest severity will be presented. If a patient reported more than one AE within the same primary SOC, the patient will be counted only once with the greatest severity at the SOC level, where applicable.

These summaries will be presented separately for study periods (Treatment Period 1, Treatment Period 2, Post-Treatment Follow-up Period), and for complete treatment periods (Treatment Periods 1 and 2 and Follow-up). Separate summaries will be provided for deaths, SAEs, other significant AEs leading to discontinuation and AEs leading to study drug discontinuation.

9.5.3 Resource utilization

Data relating to resource utilization will be used for the purpose of economic evaluation which might be carried out and reported as a separate activity.

9.5.4 Pharmacokinetics

Exploratory analysis to investigate the correlation between the PK data and efficacy outcomes will be performed. An indirect response model, driven by study drug concentration, will be used to characterize the time course of PASI response. Further details of the modeling approach will be specified in a modeling plan.

9.5.5 Pharmacogenetics/pharmacogenomics

Not applicable.

9.5.6 Biomarkers

Not applicable.

9.6 Interim analyses

No interim analysis is planned for this study.

9.7 Sample size calculation

Based on the pooled data from the CAIN457A program (CAIN4572302 and CAIN4572303), the PASI 90 response rate for biologics-naïve patients treated with secukinumab 300 mg s.c. was 74.3% at 24 weeks. Of those who were PASI 90 responders at Week 24, 81.8% of patients maintained their PASI 90 response until Week 52.

It is assumed that a dosing frequency of 6 weeks (Group 2) will differ in PASI 90 response up to 7% worse compared a dosing frequency of 4 weeks (Group 1). This assumption of a difference of maximally 7% is based on simulation of the PK levels obtained with maintenance treatments of secukinumab 300 mg every 6 weeks and the correlation between plasma levels and the clinical response seen in the secukinumab Phase 3 studies.

A total of 554 patients per group are required to achieve 90% power on a one-sided, 2.5% significance level to demonstrate the non-inferiority of 6-weekly vs 4-weekly dosing, if the true maintenance rates are 81.8% under 4-weekly and 74.8% under 6-weekly dosing and the non-inferiority margin is predefined as -15%.

The response rates underlying this estimation were obtained from pooled data of studies analyzed according to the ITT-principle using the same algorithm to handle drop-outs or protocol violations as in this present study. Therefore, the effect of drop-outs or protocol violations should be already accounted for in the effect estimates and no further adjustments of the sample size are required. However, to account for the fact that there might be minor differences (eg with respect to drop-out rates) between the historical data and the data to be observed in this study, the sample size will be rounded up slightly to 570 patients/group who should be randomized to Group 1 or Group 2 (giving a total of 1140 patients in both groups) of this study.

Assuming a PASI 90 response rate of 74% at Week 24, 1580 patients should be enrolled at Baseline in this study in order to achieve the required sample size for randomization at Week 24. This number still allows for some drop-out patients or patients withdrawing consent at or after randomization even after experiencing a PASI 90 response.

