9.4.3 Choice of the non-inferiority margin

Non-inferiority is defined as a difference in PASI 90 maintenance rate between 4- and 6-weekly dosing not exceeding 15% on a rate difference scale. Data from a pooled CAIN457A database (CAIN4572302 and CAIN4572303) suggest that the PASI 90 maintenance rate at Week 52 under 4-weekly dosing might be 81.8%. However, since the logistic regression model used for the primary analysis provides estimates on the odds-ratio scale, the numbers above have to be translated into this scale. Inserting these numbers into the respective formulas results in a non-inferiority-margin on the odds-ratio-scale of $1+\delta=2.23$. Non-inferiority of 6-weekly vs 4-weekly dosing will be claimed, if the upper limit of the CI for the odds ratio does not exceed 2.23.

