#### 1.8.2 Statistical hypothesis, model, and method of analysis

The statistical null-hypothesis to be rejected in the primary analysis is that the odds ratio of maintaining a PASI 90 response for patients with secukinumab 4-weekly dosing versus patients on secukinumab 6-weekly dosing exceeds the non-inferiority margin of  $1+\delta$ .

The primary hypothesis is stated as follows:

Let  $\pi_j$  denote the probability of a PASI 90 response at Week 52 for dosing group j, j=0, 1, where

- 0 corresponds to 4-weekly dosing
- 1 corresponds to 6-weekly dosing

The following hypothesis will be tested

$$H_{01}$$
:  $(\pi_0 / (1 - \pi_0)) / (\pi_1 / (1 - \pi_1)) \ge 1 + \delta$  versus  $H_{A1}$ :  $(\pi_0 / (1 - \pi_0)) / (\pi_1 / (1 - \pi_1)) < 1 + \delta$ 

The non-inferiority margin  $1+\delta$  is calculated as 2.23 assuming a PASI 90 response maintenance rate of 81.8% under 4-weekly dosing treatment scheme and using a 15% non-inferiority margin. The **primary analyses** will be performed comparing dosing groups (Group 1 vs. Group 2) with respect to the primary efficacy variable in a logistic regression model with the factors dosing group, country, PASI 90 response at Week 16 (Yes, No) and body weight at Week 24 (< 90 kg or  $\geq$  90 kg, for model definition see Section 2.2.2). The odds ratios and their two-sided 95%-Wald confidence intervals (CIs) will be given.

In case of subgroup analyses where the grouping variable is one of the above described factors in the logistic regression model the respective factor is excluded from the model.

Additionally, the one-sided p-value for the shifted null-hypothesis will be given. The respective test statistic is calculated as

$$\frac{\hat{\beta}-\beta_0}{se_{\hat{\beta}}}$$

where  $\hat{\beta}$  is the type 3 maximum likelihood estimate of the dosing group parameter in the logistic regression model and  $se_{\hat{\beta}}$  is its standard error.  $\beta_0$  is the non-inferiority margin of the estimator which corresponds to the  $\delta$  from the above null-hypothesis and is therefore set to  $ln(1+\delta) = ln(2.23) = 0.80$ .

Only in case that the number of patients with response (or non-response) in one of the groups is 5 or lower, exact logistic regression will be used for the primary analysis instead of logistic regression using maximum-likelihood based estimators.

The primary analysis set will be the FAS-P90R.

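### The 90% power with 554 per group belongs to a risk-difference test; the odds-ratio rule that decides non-inferiority has about 75% power, unadjusted, at the plan's 7-point worst case

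*Protocol*

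**What the plan says.** The sample size section (Protocol 9.7, SAP 1.11) gives its result as "A total of 554 patients per group are required to achieve 90% power on a one-sided, 2.5% significance level", "if the true maintenance rates are 81.8% under 4-weekly and 74.8% under 6-weekly dosing and the non-inferiority margin is predefined as -15" per cent. The 7-point gap between the two rates is put forward as a ceiling: "This assumption of a difference of maximally 7" per cent, taken from PK simulation. The figure is then rounded up to 570 per group because "there might be minor differences (eg with respect to drop-out rates) between the historical data and the data to be observed in this study".

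The decision is made on another scale. Protocol 9.4.3 defines the margin as 15 points on the rate difference, notes that the primary model works with odds ratios so that "the numbers above have to be translated into this scale", and claims non-inferiority "if the upper limit of the CI for the odds ratio does not exceed 2.23". SAP 1.8.6 repeats this rule and specifies a two-sided 95% Wald interval. The interval comes from a "logistic regression model with the factors dosing group, country, PASI 90 response at Week 16 (Yes, No) and body weight at Week 24" (SAP 1.8.2).

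The risk difference is supportive only. Protocol 9.4.5 says "The raw (unadjusted) response rates and their difference will be computed with the corresponding CI", and SAP 1.8.4 lists it among the sensitivity analyses. Neither document gives a power figure for the odds-ratio rule.

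**The concern.** The margin was converted to the odds-ratio scale; the power was not. Two margins that coincide at one control rate do not make two tests equally powerful. When the control rate is high and the true loss is about half the margin, the Wald test on the log odds ratio sits fewer standard errors from its limit than the risk-difference test does.

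If so, the 90% is not a property of the test that decides the trial, at the only scenario for which the plan claims it. The planned 570 per group and the enrolment of 1580 both rest on that calculation. The key secondary comparison is confirmatory only if the primary succeeds (SAP 1.8.6), so its chance of a confirmatory claim is overstated as well. A narrow failure on the primary could also be read too strongly as evidence against 6-weekly dosing by anyone relying on 90% power.

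**Working it through.** **Inputs.** One-sided 2.5%, power 90%, rates 0.818 and 0.748, margin 0.15, and 554 rounded up to 570 per group (Protocol 9.7); 1:1 allocation (Protocol 3.1); odds-ratio limit 2.23 (Protocol 9.4.3, SAP 1.8.6).

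**1. Reproduce 554.** Unpooled risk-difference formula, with distance to the margin 0.15 − 0.07 = 0.08:

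n = (1.96 + 1.2816)² × (0.818×0.182 + 0.748×0.252) / 0.08² = 553.9, so 554.

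The documents do not name the test, but this formula returns the stated number. Other risk-difference variants come close without matching: Farrington-Manning 556, pooled variance 557, continuity-corrected 579. Power of the unpooled test is 90.0% at 554 and 90.8% at 570 (89.6% at 570 with continuity correction).

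**2. Reproduce 2.23.** (0.818/0.182) / (0.668/0.332) = 2.234. The conversion is correct at a control rate of 81.8%.

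**3. Power of the deciding rule, without covariates.** The true odds ratio at the planned rates is (0.818/0.182) / (0.748/0.252) = 1.514.

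- SE(n) = √[(1/(0.818×0.182) + 1/(0.748×0.252)) / n], which is 0.147 at 554 and 0.1452 at 570.
- Power = Φ[(ln 2.23 − ln 1.514)/SE − 1.96], which is 74.8% at 554 and 76.0% at 570.
- Full binomial enumeration of the same Wald rule gives 74.2% and 75.3%, so this is not an artefact of the normal approximation.

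**4. Where the power goes.** At 554 per group the risk-difference test lies 0.08/0.0247 = 3.24 SE from its margin. The odds-ratio test lies 0.387/0.147 = 2.63 SE from its limit. Rounding up to 570 does not close the gap: the odds-ratio rule would need about 843 per group for 90% power at this scenario, and about 630 for 80%.

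**5. Dependence on the true loss.** Odds-ratio rule, 570 per group, control 81.8%, unadjusted:

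| True loss | Formula | Enumeration |
|---|---|---|
| 7 points | 76.0% | 75.3% |
| 6 points | 85.5% | 84.8% |
| 5 points | 92.1% | 91.6% |

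Power reaches 90% at a loss of about 5.4 points or less.

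**6. Type I error.** At 81.8% against 66.8% the unadjusted rule passes 2.46% of the time by enumeration.

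**7. Covariate adjustment (assumed inputs only).** The documents give no covariate effects. With the marginal rates held at 81.8% and 74.8%, adjustment for a prognostic factor moves the conditional odds ratio away from 1 and raises its standard error, while the limit stays at 2.23.

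- One binary covariate, prevalence 80%, odds ratio 2, 3 or 4: power at 570 and 7 points is 74%, 70% and 66% by formula (simulation 73%, 69%, 64%). At 6 points it is 84%, 81% and 78%; at 5 points 91%, 90% and 87%. Over prevalences of 70% to 90% the 7-point range is 64% to 75%.
- A fuller simulation assumed 12 countries, 85% PASI 90 response at Week 16 and 45% of patients at or above 90 kg, with 1500 runs per setting. At 570 and 7 points it gave about 74% with no covariate effect, 65% with modest, 58% with moderate and 47% with strong effects.

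These show a direction, not a value.

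**The case against.** The strongest reply is that nothing has been miscalculated. Both 554 and 2.23 follow from their stated inputs, and Protocol 9.7 says openly that its margin is 15 points. The 7 points are a ceiling, and at a 5-point loss the unadjusted odds-ratio rule already has about 92% power. A positive result is valid, and no analysis would change. Moreover, the 75% is itself the power of an unadjusted two-by-two rule, not of the planned model, and the covariate scenarios rest on inputs found nowhere in the documents. Finally, SAP 1.8.2 already says that 2.23 assumes 81.8%, and the risk difference is already planned.

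Much of this is fair. The fault is a mismatch between the test used for sizing and the test used for deciding, not a slip in either calculation. The effect is smaller if the true loss is below the ceiling. The adjusted figures depend heavily on what is assumed, as the distance between the two sets shows, so they cannot stand as estimates. The sentence on 2.23 is a clarification and not a correction.

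None of it rescues the stated power. The plan claims 90% at exactly a 7-point loss, and there the deciding rule falls well short. That the 75% is unadjusted is met by labelling it so; with the marginal rates fixed, adjustment does not bring the power back up.

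**Conclusion.** The concern holds. The 90% in Protocol 9.7 and SAP 1.11 does not describe the planned primary test. At 81.8% against 74.8%, the odds-ratio rule has about 75% to 76% power at 570 per group, some 15 points below the 90.8% of the risk-difference test with the same numbers. This rests only on the plan's own rates, limit and sample size, and on leaving covariates out. The planned model is likely to have somewhat less power, by an amount that cannot be settled from the documents. The error concerns the stated chance of success; the unadjusted check shows no inflation of the type I error. It should be corrected because it is a headline design figure and the correction is simple.

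**What to change.** In Protocol 9.7 and SAP 1.11, state that 554 per group and 90% power refer to an unadjusted risk-difference test with a 15-point margin. Then add the power of the deciding rule, for example:

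> For the confirmatory criterion (upper 95% Wald limit of the odds ratio not above 2.23), 570 patients per group give a power of about 75% if the true loss is 7 points, about 85% at 6 points and about 92% at 5 points, with a 4-weekly rate of 81.8%. These figures are unadjusted; the covariate-adjusted model may have lower power.

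As a clarification only, add one sentence to Protocol 9.4.3 and SAP 1.8.2: 2.23 equals 15 points only near a control rate of 81.8% (for assumed control rates of 80% and 85% it equals 15.8 and 13.2 points), so the planned risk difference and its interval should be read beside the odds ratio.

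The cost is text in four places. One stated figure becomes less favourable; the confirmatory rule, margin, analyses and enrolment target stay as they are.

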9.7.1 Power for the key secondary objective

As per the sample size calculation for the primary objective, 1580 patients will be enrolled into Phase 1 of the study. In the secukinumab database (CAIN457A2302 and CAIN457A2303) 13.3% of patients were in the category of PASI 75 but did not achieve PASI 90 at Week 24. In the present study, this would translate into 210 patients fulfilling the criteria to be randomized into the partial responder part of the maintenance phase.

Prior Phase 3results (CAIN457A2302 and CAIN457A2303) suggest that the PASI responses reach a maximum at around 16 to 24 weeks with a sustained effect until Week 52. The PASI 90 responder rate at Week 52 of patients treated with secukinumab 300 mg s.c. every 4 weeks who have a PASI 75 but no PASI 90 response at Week 24 is estimated to be 3.8%. This rate may be increased by 14% (to then 18%) by increasing the dosing frequency to 2-weekly after Week 24.

A sample size of 210 patients (105 per group) will provide more than 90% power on a twosided, 95% significance level to detect differences in response rates for secukinumab intensified 2-weekly dosing compared to every 4 weeks, if the responder rates in these groups are about 4% vs. 18% at Week 52.

10 **Ethical considerations**

10.1 Regulatory and ethical compliance

This clinical study was designed and shall be implemented and reported in accordance with the International Conference on Harmonization of Technical Requirements for Registration of Pharmaceuticals for Human Use (ICH) Harmonized Tripartite Guidelines for GCP, with applicable local regulations (including European Directive 2001/20/EC, US CFR 21, and Japanese Ministry of Health, Labor, and Welfare), and with the ethical principles laid down in the Declaration of Helsinki.

10.2 Informed consent procedures

Eligible patients may only be included in the study after providing written (witnessed, where required by law or regulation), IRB/IEC-approved informed consent, or, if incapable of doing so, after such consent has been provided by a legally acceptable representative of the patient. In cases where the patient's representative gives consent, the patient should be informed about the study to the extent possible given his/her understanding. If the patient is capable of doing so, he/she should indicate assent by personally signing and dating the written informed consent document or a separate assent form. Informed consent must be obtained before conducting any study-specific procedures (ie, all of the procedures described in the protocol). The process of obtaining informed consent should be documented in the patient source documents.

Novartis will provide to Investigators in a separate document a proposed ICF that complies with the ICH GCP guideline and regulatory requirements and is considered appropriate for this study. Any changes to the proposed consent form suggested by the Investigator must be agreed to by Novartis before submission to the IRB/IEC, and a copy of the approved version must be provided to the Novartis monitor after IRB/IEC approval.

Women of child bearing potential should be informed that taking the study drug may involve unknown risks to the fetus if pregnancy were to occur during the study and agree that in order to participate in the study they must adhere to the contraception requirement for the duration of the study. If there is any question that the patient will not reliably comply, they should not be entered in the study.

10.3 Responsibilities of the Investigator and IRB/IEC

Before initiating a study, the Investigator/institution should obtain approval/favorable opinion from the Institutional Review Board/Independent Ethics Committee (IRB/IEC) for the study protocol, written ICF, consent form updates, patient recruitment procedures (eg, advertisements) and any other written information to be provided to patients. Prior to study start, the Investigator is required to sign a protocol signature page confirming his/her agreement to conduct the study in accordance with these documents and all of the instructions and procedures found in this protocol and to give access to all relevant data and records to Novartis monitors, auditors, Novartis Clinical Quality Assurance representatives, designated agents of Novartis, IRBs/IECs, and regulatory authorities as required. If an inspection of the study center is requested by a regulatory authority, the Investigator must inform Novartis immediately that this request has been made.

